### **Statistical analysis**

Quantitative variables are presented as medians (ranges) or means  $\pm$  standard deviations and were analysed using the Mann-Whitney U test or t-test as appropriate. Categorical variables are reported as absolute numbers and proportions and were tested by the chi-square test or Fisher's exact test as appropriate. The differences between outcomes for matching data were tested with the paired t test or Wilcoxon signed-rank test as appropriate. We estimated relative risks (RRs) and 95% confidence intervals (CIs) for primary outcomes and secondary outcomes. A two-tailed P value  $<0.05$  was considered statistically significant. Data were analyzed using SPSS software (v17.0; SPSS Inc., Chicago, IL, USA).

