### **Introduction**

Acute pancreatitis (AP) is a acute inflammatory disease of the pancreas. The incidence of AP ranges from 5 to 30 cases per 100,000, with an overall case fatality rate of 5%. Approximately 80% cases of AP are mild and self-limited, and about 20% of patients suffer a severe disease course with persistent organ failure and/or infected pancreatic necrosis (IPN), with a mortality risk as high as 20~30%.

Gastrointestinal tract is considered not only as a target organ during systemin inflammatory response syndrome (SIRS) and multiple organ dysfunction syndrome (MODS), but also a “motor organ” of gut-derived infection. Gastrointestinal dysfunction has been proven to be associated with adverse outcomes in AP.

Although the mechanisms underlying gastrointestinal dysfunction in the early phase of AP is complicated, early gastrointestinal barrier dysfunction was considered to be the main cause. Gastrointestinal microbiota dysbiosis induces the injury of biologic barrier, which plays a key role in the pathogenic of gut-driven infection. Therefore, the maintenance of gastrointestinal microecology balance may be an effective method in treating gastrointestinal dysfunction, preventing gut-driven infection and improve clinical outcomes in AP.

Probiotics, as an adjunct to enteral nutrition, has long been studied as a measure to improve intestinal barrier dysfunction and prevent secondary infection in AP. Several clinical studies have assessed the effect of probiotics prophylaxis with contradictory results, and significant heterogeneity was noted between the trials with regard to the

type, dose and treatment duration of probiotics. A multicenter, double-blind, placebo-controlled trial have failed to show a beneficial effect of probiotic prophylaxis on the occurrence of infectious complications, and mortality in the probiotics group was about twice as high as in the placebo group. The current data are not sufficient to draw a conclusion regarding the effects of probiotics on patients with predicted severe acute pancreatitis (SAP). Consequently, there is a clear need for other innovative strategies.

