### **Exclusion criteria**

- 1) Complicated by gastrointestinal bleeding or intestinal fistula;
- 2) Pregnancy and lactation women;
- 3) Not signed the informed consent;

- 4) Diabetes and autoimmune disease;
- 5) Multiple organ failure, which was defined as two or more organ failure including respiratory failure, renal failure or circulatory failure, which was defined as a score of 2 or more using the modified Marshall scoring system^17.

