### **Secondary endpoints**

The secondary end points were any infectious complication, OF, functional assessments of gut barrier and inflammatory indicators, hospital stay and mortality. Infectious complications included IPN, infected ascites, bacteremia, pneumonia, urinary tract infection. Microbiological data for each of the infectious complications were collected. OF was defined as a score of 2 or more using the modified Marshall scoring system, which was recommended by 2012 Atlanta Classification Creation. Persistent organ failure, that is, organ failure >48 hours. Blood samples were collected from all included patients before and one week after intervention. Gut barrier function was assessed by detecting serum D-Amino Acid Oxidase (DAO) and endotoxin using commercial kits (Cloud-Clone Corp, TX, USA for DAO and ELX800 (Bio Tek) for endotoxin). C-reactive protein (CRP) and procalcitonin (PCT) were measured by IMMAGE 800 (Beckman Coulter) and AFIAS-50 (JOINSTAR) separately. Stools were requested for microbiota analysis at baseline, one week and two week after intervention.

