### **Data collection**

Data collection was prospectively entered by a researcher, who completed standardized case report forms. During the study an independent data monitor checked the individual patients' data against the primary source data. After double check of key variables by two researchers, data were exported unedited for statistical

analyses.

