### **Follow up**

Patients are followed during their hospital stay. There is one follow-up visit, 6 months after discharge by clinical visit or telephone visit, to assess readmission, mortality and adverse events.

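### Does the plan need a written rule for how a hospital stay that ends in death enters the between-group comparison?

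*Combined protocol and SAP*

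**What the plan says.** In the combined protocol and SAP, the Secondary endpoints section lists, among others, "functional assessments of gut barrier and inflammatory indicators, hospital stay and mortality". Stay and mortality are therefore two separate endpoints.

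The Statistical analysis section does not name hospital stay. By variable type it falls under the rule for quantitative variables, which reads in part "standard deviations and were analysed using the Mann-Whitney U test or t-test as appropriate".

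On data, the Data collection section states "Data collection was prospectively entered by a researcher, who completed standardized case report forms" and adds that the checked data went to analysis without editing. It does not list the fields on the forms. The Follow up section covers the hospital stay and then one later contact: "There is one follow-up visit, 6 months after discharge by clinical visit or telephone visit, to assess readmission, mortality and adverse events". None of these sections says how a stay that ends in death is counted.

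**The concern.** Patients who die in hospital have a length of stay, but it does not mean what a survivor's stay means. Entered raw, a death on day 5 scores like a live discharge on day 5. An arm with more early deaths then looks better on stay, and an arm with more late deaths looks worse. Leaving deaths out instead conditions the comparison on survival, which is itself an event after randomisation.

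Deaths are foreseeable in this population. The Introduction describes acute pancreatitis "with an overall case fatality rate of 5" per cent and gives 20–30% for a severe course. It also reports that in one placebo-controlled trial of a related therapy "mortality in the probiotics group was about twice as high as in the placebo group". At stake would be a misleading result on one secondary endpoint, and an analyst's freedom to choose between two readings after seeing the data.

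**Working it through.** The plan gives no figure for length of stay, mortality by arm or timing of death, so there is no stated number to reproduce. The check asks how far the unstated rule could move the result.

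**Inputs from the documents.** 30 patients per arm (Sample size); two-tailed 5% level (Statistical analysis); 5% overall fatality and 20–30% in severe disease (Introduction).

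**Assumptions, not in the documents.** Survivors' stay is lognormal with median 21 days and log-SD 0.5, the same in both arms. Mortality is 10% with FMT against 5% with control, or 20% against 10%. The day of death is uniform over a window, with the same window in both arms.

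**Expected deaths.** FMT against control: 30 × 0.10 = 3 against 30 × 0.05 = 1.5, or 30 × 0.20 = 6 against 30 × 0.10 = 3.

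**Mean survivor stay.** 21 × exp(0.5²/2) = 21 × 1.133 = 23.8 days.

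**Shift in mean raw stay (FMT minus control).** (FMT mortality − control mortality) × (mean day of death − 23.8). For deaths on days 2–12 the mean day of death is 7, so the shift is 0.05 × (7 − 23.8) = −0.84 days, or 0.10 × (7 − 23.8) = −1.68 days. The rejection rates below come from 20,000 simulated trials per cell, using a two-sided 5% Mann-Whitney test on raw stay.

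| Days of death (mean) | Shift, 10% v 5% | Shift, 20% v 10% | Two-sided rejection, 10% v 5% | Two-sided rejection, 20% v 10% |
|---|---|---|---|---|
| 2–12 (7) | −0.84 | −1.68 | 6.1% | 9.3% |
| 2–30 (16) | −0.39 | −0.78 | 5.1% | 5.6% |
| 2–45 (23.5) | −0.02 | −0.03 | 4.7% | 5.1% |
| 10–60 (35) | +0.56 | +1.12 | 5.2% | 6.1% |

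In the worst cell, FMT is falsely declared shorter in 8.8% of trials, against a nominal 2.5% in that direction.

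**Shift against noise.** The SD of survivor stay is 23.8 × √(exp(0.25) − 1) = 12.7 days. The standard error of the difference in means is about 12.7 × √(2/30) = 3.3 days. The largest shift is 1.68/3.3, about half a standard error.

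**A second death-time model.** With lognormal death times (median day 7, 4,000 trials), the arm with more deaths is 0.8 or 1.6 days shorter and the rejection rate is 5.0% or 7.9%. With median day 30 the sign reverses, to 0.6 or 1.1 days longer, with 5.0% or 4.8% rejection.

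**Survivors only.** There is no bias if death is unrelated to the stay the patient would have had. At a correlation of 0.5 between risk of death and log potential stay, FMT looks 0.6 or 0.9 days shorter and is declared shorter in 3.6% or 4.5% of trials.

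**Choosing between readings.** Raw and survivors-only results disagree on significance in 2.9–9.4% of trials. With equal mortality, keeping whichever is significant raises the two-sided error to 6.2–7.3%.

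**Deaths ranked worst.** With survivors' stay identical, this test rejects in 6.1–6.3% (10% v 5%) or 10.0–10.4% (20% v 10%) of trials whatever the timing of death, mostly against the arm with more deaths. With equal mortality it holds 5.0–5.2%.

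**The case for a change.** The strongest argument for a change is the open choice more than the size of the bias. Two defensible analyses of one endpoint can disagree, and choosing between them inflates error even when mortality is equal. One sentence would settle it and needs only the length of stay and the discharge status. The bias also grows if mortality reaches the severe range: at 30% against 15%, with deaths at a median of day 7, raw stay is 2.4 days shorter in the arm with more deaths and the test rejects in 12.7% of trials.

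Part of this stands. The rule is unwritten, and stating one would do no harm. The rest carries less weight:

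- **Selection.** The error of 6.2–7.3% requires someone to run both readings and keep the better one. Under Randomization and masking, the allocation key is opened only after the data analysis is complete. That limits picking in favour of one arm, though a masked analyst could still chase any significant result. Nothing in the plan suggests leaving deaths out, and sending unedited data to analysis fits raw stay.
- **Mortality.** The Exclusion criteria remove "Multiple organ failure, which was defined as two or more organ failure", so rates of 20–30% are probably too high here. The doubled mortality comes from one probiotic trial, about which the Introduction says "The current data are not sufficient to draw a conclusion regarding the effects of probiotics". It is a possibility to bear in mind and does not predict the effect of FMT.
- **Remedy.** Ranking deaths worst changes the question, gives no difference in days and partly duplicates the mortality endpoint. Survivors-only analysis and discharge alive with death as a competing event are rivals on which statisticians reasonably differ. Days alive and out of hospital would need dates that the single six-month contact is not said to collect.

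**Conclusion.** No change to the plan is needed. The omission is genuine, but it is a gap that analysts fill sensibly: raw stay is compared and read beside mortality by arm. Any excess of deaths is then visible, and a shorter stay in the arm with more deaths would not be mistaken for benefit. On the assumed values the distortion is at most about half a standard error, its direction is unknown without death timing, and the error rate is clearly raised in one of eight scenarios (9.3%, with 20% against 10% mortality and all deaths by day 12). The primary endpoint and the sample size are untouched. The more elaborate alternatives trade one limitation for another.

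This rests on the assumed survivor stay, mortality and death windows, none of which the documents give, and on mortality staying below the severe-disease range. Much higher and unequal mortality with early deaths would make raw stay hard to interpret, but the mortality endpoint would then be the result that matters.

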### **Inclusion criteria**

- 1) Aged 18-70 year;
- 2) Onset of pancreatitis within 2 weeks;
- 3) Complicated with gastrointestinal failure, which was defined if the patients were complicated with obvious abdominal distention, abdominal rumbling sound weakening or disappearance, no self-defecation as well as intra-abdominal hypertension (IAH).

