### **Sample size**

To detect a minimal clinically relevant difference of 35% between FMT group and control group in the primary outcome, and estimating that FMT would achieve 85% power and control would achieve 50% power and using a type I error of 0.05 and a type II error of 0.20 (80% power), we calculated that a minimal sample size of 48 with 24 patients in each group was required. To allow for dropouts, we included 60 participants with 30 in FMT group and 30 in control group.

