### **Primary Endpoint**

The primary end point was the recovery of gastrointestinal dysfunction assessed by GIF score one week after intervention. The normal gastrointestinal function assessed by GIF score means enteral feeding >50% of calculated needs, without FI and IAH. FI was defined when applied enteral feeding appeared to be unsuccessful

and had to be discontinued because of repeated or profuse vomiting, high gastric residuals, ileus, severe diarrhea, abdominal pain, or distension. FI should not be considered as present if enteral feeding is electively not prescribed or is withheld/interrupted due to procedures. IAP was measured by the standardized methodology (preferably the transvesical method, with a maximal instillation of 25 cc of saline in the supine position, measured at the end of expiration, with zeroing done at the level of the midaxillary line). IAH was present if the IAP was found to be 12 mmHg or higher, as confirmed by at least two measurements taken 1-6 h apart.

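### The primary analysis is valid but unadjusted: it makes no use of baseline intra-abdominal pressure, the starting value of one component of the endpoint, so precision may be lost

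*Combined protocol and SAP*

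**What the plan says.** The Primary Endpoint section reads: "The primary end point was the recovery of gastrointestinal dysfunction assessed by GIF score one week after intervention". Normal function has three parts: feeding above half of calculated needs, no feeding intolerance, and no intra-abdominal hypertension (IAH). The same section defines the last part by measurement: "IAH was present if the IAP was found to be 12 mmHg or higher", confirmed by at least two readings.

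The Inclusion criteria require IAH at entry and "Onset of pancreatitis within 2 weeks". They set no upper limit on IAP.

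The Statistical analysis section is the whole analysis plan. For a binary outcome it states: "Categorical variables are reported as absolute numbers and proportions and were tested by the chi-square test" or Fisher's exact test, and adds relative risks (RRs) with 95% intervals. It names no covariate, regression model or stratified analysis. Randomization and masking describes a 1:1 list for 60 participants and names no stratification factor.

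The Sample size section rests on an unadjusted comparison: "To detect a minimal clinically relevant difference of 35% between FMT group and control group in the primary outcome", with "FMT would achieve 85% power and control would achieve 50% power". The two percentages can only be read as recovery rates. It arrives at 24 per arm, raised to 30 for dropout.

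**The concern.** Patients may enter just above 12 mmHg or far above it. Those who start high have further to fall before they can count as recovered. This makes baseline IAP a more specific candidate for adjustment than a general severity marker: it is measured on the scale that decides part of the outcome.

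With about 30 per arm and no stratification, neither design nor analysis uses this information. If IAP predicts recovery, an adjusted estimate of the treatment effect has a narrower interval with no extra patients. If the arms happen to differ in baseline IAP and no adjustment was prespecified, any adjustment made later is open to the charge that the covariate was chosen after seeing the data.

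**Working it through.** **Inputs from the documents.** Recovery 0.85 vs 0.50, difference 0.35, alpha 0.05 two-sided, power 80%, 24 evaluable and 30 enrolled per arm.

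**The plan's own figure.** Two proportions, unpooled variance:

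n = (1.960 + 0.842)² × [0.85×0.15 + 0.50×0.50] / 0.35² = 24.19 per arm.

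The stated 24 is reproduced to within rounding. It contains no allowance for a covariate.

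**Power of the named tests (exact enumeration).** Chi-square: 76.7% at 24 per arm and 84.7% at 30. Fisher: 66.8% and 77.7%.

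**Approximate effect of adjustment.** If baseline covariates explain a share R² of the outcome variance, the variance of the treatment effect is multiplied by about (1 − R²), so n behaves like n/(1 − R²). R² is an assumption; the documents give no value. Using the pooled-variance power formula:

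| Assumed R² | Power, 24 per arm | Power, 30 per arm |
|---|---|---|
| 0 | 75.1% | 84.3% |
| 0.10 | 79.6% | 88.0% |
| 0.15 | 82.0% | 89.8% |
| 0.20 | 84.3% | 91.5% |

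This ignores the cost of estimating the covariate effect, so simulation is needed at these sizes.

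**Simulation, logistic regression on arm and IAP alone, standardised to a marginal risk difference.**

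| Assumed strength of IAP | Per arm | Adjusted | Chi-square | Difference |
|---|---|---|---|---|
| Unrelated | 24 | 75.8% | 76.5% | −0.7 |
| Unrelated | 30 | 84.1% | 83.7% | +0.4 |
| Moderate | 24 | 83.5% | 76.9% | +6.6 |
| Moderate | 30 | 90.8% | 85.4% | +5.4 |

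Rejection under the null was about 5-6%, similar to chi-square. In the moderate case the variance fell by 12-15%. The interval is then √0.88 = 0.94 to √0.85 = 0.92 of its unadjusted width. At 30 per arm this is worth 30/0.88 = 34 to 30/0.85 = 35 patients per arm.

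**Same method with days since onset added** (4000 runs per setting; IAP exponential above its threshold and days uniform, both assumed). At 30 per arm, adjusted vs chi-square power was:
- R² 0: 84.7 vs 84.9%
- R² 0.04: 85.2 vs 83.4%
- R² 0.10: 87.7 vs 85.4%
- R² 0.165: 89.9 vs 84.7%
- R² 0.27: 93.4 vs 85.2%

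The variance ratios were 1.03, 1.00, 0.97, 0.88 and 0.81. Weak covariates therefore bring little or nothing. Monte Carlo error on each power is about 0.6 points.

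**Linear model with HC3 errors and both covariates, unrelated to recovery.** Two separate runs gave 82.6 vs 84.9% and 82.2 vs 84.8% at 30 per arm, a loss of 2.3 to 2.6 points. At 24 per arm they gave 70.0 vs 75.4% and 72.4 vs 77.2%, a loss of 4.8 to 5.4 points. Part of the gap at 24 arises because chi-square is slightly liberal there.

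**Model size.** Expected non-recoveries are 24×0.15 + 24×0.50 = 15.6 at 24 per arm, and 30×0.15 + 30×0.50 = 19.5 at 30. That supports arm plus one covariate better than a longer list.

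**The case against.** The strongest objection is that nothing here is an error. The unadjusted test is valid under 1:1 randomisation and matches the basis of the sample size. A reader might infer that chance imbalance in IAP biases the result. It does not: the test and its interval already allow for chance imbalance. This stands in full.

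A reader might also infer that precision is certainly being lost. The documents do not support that. They give no prognostic strength for IAP. Entry truncates it at 12 mmHg, and absence of IAH is only one of three conditions for recovery. Both facts may weaken the association. For days since onset, nothing in the documents links it to recovery, and entry truncates it at two weeks. This is why it is only an optional second covariate.

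Third, it is tempting to say that baseline IAP is already in the data. No section lists it as a recorded analysis variable. That it must be measured follows from the entry criterion, if the IAH definition given under Primary Endpoint also applies at entry. Since IAH needs at least two readings, the baseline value also has to be defined.

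Finally, adjustment is not free under every method. The loss with the two-covariate HC3 model is real, and largest at the evaluable size that the plan itself allows for. It does not carry over to standardised logistic regression on IAP alone, where the cost of a useless covariate is within about one point.

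**Conclusion.** The point holds as an improvement in efficiency, not as the correction of a fault. The plan leaves unused a baseline measurement that its own entry criterion requires and that is tied directly to its endpoint, so precision may be lost. At 24-30 per arm, standardised logistic adjustment for IAP changes power by about 0 to −1 point if IAP is unrelated to recovery. It adds about 5 to 7 points, with 12-15% lower variance, if IAP is moderately prognostic. These figures assume recovery of 85% vs 50%; the strength of IAP and the covariate shapes are also assumptions. The small cost if IAP proves uninformative, against the possible gain, justifies making the change.

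**What to change.** Before allocation is linked to outcomes, replace the primary-analysis wording along these lines:

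- **Primary:** marginal risk difference and RR for recovery at one week, from logistic regression on arm and baseline IAP (continuous), standardised over all analysed patients, with robust standard errors and 95% intervals.
- **Baseline IAP:** define it in advance, for example as the mean of the qualifying pre-intervention readings, and confirm that the case report form records it. State how a missing value is handled.
- **Optional second covariate:** days since onset, decided in advance.
- **Fallback:** use the unadjusted comparison if the model cannot be fitted, for example if every patient in one arm recovers. At a true rate of 85% this has probability 0.85^24 = 2.0% at 24 per arm and 0.85^30 = 0.8% at 30.
- **Supportive:** one unadjusted test, with the choice between chi-square and Fisher fixed in advance.
- **Not the default:** the linear model with HC3 errors and two covariates.

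The cost is a short piece of analysis text, the definition of the baseline reading and a check of the case report form. If the named SPSS version cannot produce the standardised estimate, the software must be named as well. No patients or visits are added, and the plan's own effect measure, the RR, is kept.

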### **Microbiomics analysis**

Fecal samples were longitudinally collected from patients at baseline before first FMT, one weeks and two weeks after first FMT. The fresh feces were collected in sterile cryopreservation tube by the nurses and kept at -20 °C immediately. Then, the feces were transferred within 6 hour after a bowel movement, and were stored at -80 °C until DNA extraction.

Bacterial DNA was extracted from fecal samples using the E.Z.N.A. Soil DNA Kit (Omega Bio-Tek, Norcross, GA, USA) according to the manufacturer's instructions. The final DNA concentration and purification were determined by NanoDrop 2000 UV-vis spectrophotometer (Thermo Scientific, Wilmington, USA), and DNA quality was checked by 1% agarose gel electrophoresis. The V3-V4 hypervariable regions of the bacteria 16S rRNA gene were amplified with primers 338F (5'-ACTCCTACGGGAGGCAGCAG-3') and 806R (5'-GGACTACHVGGGTWTCTAAT-3') by thermocycler PCR system (GeneAmp 9700, ABI, USA). The PCR reactions were conducted using the following program: 3 min of denaturation at 95°C, 27 cycles of 30 s at 95°C, 30 s for annealing at 55°C, and 45 s for elongation at 72°C, and a final extension at 72°C for 10 min. PCR reactions were performed in triplicate 20 µL mixture containing 4 µL of 5 × FastPfu Buffer, 2 µL of 2.5 mM dNTPs, 0.8 µL of each primer (5 µM), 0.4 µL of FastPfu Polymerase and 10 ng of template DNA. The resulted PCR products were extracted from a 2% agarose gel and further purified using the AxyPrep DNA Gel Extraction Kit (Axygen Biosciences, Union City, CA, USA) and qualified using QuantiFluro-ST (Promega, USA).

Purified amplicons were pooled in equimolar and paired-end sequenced (2×300) on an Illumina MiSeq platform (Illumina, San Diego, USA). The raw reads were deposited into the NCBI Sequence Read Archive (SRA) database (Accession Number: SRP). The raw reads were demultiplexed and quality-filtered by Trimmomatic and merged by FLASH software. The high-quality sequences were assigned to samples according to barcodes. Operational taxonomic units (OTUs) were clustered with 97% similarity cutoff using UPARSE (version 7.1, <http://drive5.com/uparse/>) and chimeric sequences were identified and removed using UCHIME. The taxonomy of each 16S rRNA gene sequencing was analyzed by RDP Classifier algorithm (<http://rdp.cme.msu.edu/>) against the Siva (SSU123) 16S rRNA database using confidence threshold of 70%.

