### **General treatment regimen**

All participants received routine treatment at admission according to the AP guidelines, including goal-oriented fluid resuscitation, enteral nutrition as early as possible, organ support as needed. Antibiotic prophylaxis was not given routinely. The use of antibiotics was recorded, irrespective of indication. As all the patients enrolled was complicated with gastrointestinal failure, we used traditional Chinese medicine-rhubarb (and/or mirabilite) for all patients. Some other purge measures including gastrointestinal decompression or mannitol via nasoduodenal tube were conducted according to patients' conditions. Abdominal puncture and drainage were for patients with abdominal effusion.

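### Paired before/after tests share the P<0.05 rule with the between-arm tests, and the plan does not say which result supports a claim about FMT on blood markers or microbiota

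*Combined protocol and SAP*

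**What the plan says.** The Statistical analysis section lists three kinds of test in one paragraph.

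- Quantitative variables "were analysed using the Mann-Whitney U test or t-test as appropriate", and categorical variables "were tested by the chi-square test or Fisher's exact test as appropriate". These compare the two arms.
- For repeated data: "The differences between outcomes for matching data were tested with the paired t test or Wilcoxon signed-rank test as appropriate". The sentence names no endpoint or arm and gives the result no inferential role.
- One threshold covers everything: "A two-tailed P value" below 0.05 counts as significant.

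The paragraph also says: "We estimated relative risks (RRs) and 95% confidence intervals (CIs) for primary outcomes and secondary outcomes". A relative risk does not apply to a continuous marker, so no between-arm effect estimate is named for the markers.

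The paired data come from two places. Secondary endpoints says "Blood samples were collected from all included patients before and one week after intervention"; these samples give DAO, endotoxin, CRP and PCT. Microbiomics analysis says "Fecal samples were longitudinally collected from patients at baseline before first FMT, one weeks and two weeks after first FMT".

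On care common to both arms, General treatment regimen describes guideline-based routine treatment for everyone and adds: "we used traditional Chinese medicine-rhubarb (and/or mirabilite) for all patients".

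**The concern.** A before/after test asks whether a marker changed over the week. It does not ask whether FMT changed it more than saline did. Any change that both arms share, through routine care or the natural course, can make the before/after P value small with no FMT effect.

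For each marker the plan can thus yield a between-arm P value and one or more before/after P values, all judged at 0.05, with no statement of which one bears on FMT. A report that endotoxin fell significantly after FMT but not after saline would be easy to take as a gut-barrier effect. The Introduction makes the effect of FMT on gut microbiota a stated aim, and gut-barrier function and inflammatory markers are secondary endpoints. The ambiguity therefore reaches conclusions that the trial sets out to draw.

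**Working it through.** **1. The plan's own figure.** The paired tests have no sample-size figure of their own. The Sample size section gives 24 per arm for 85% against 50%, with two-sided alpha 0.05 and 80% power. (It calls these two percentages power; they only make sense as recovery rates.) With unpooled variance:

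n = (1.960 + 0.842)² × (0.85×0.15 + 0.50×0.50) / 0.35² = 24.19 per arm.

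This reproduces the stated 24, or 25 if rounded up. The enrolled 30 per arm matches a 20% dropout allowance: 24/0.80 = 30. Both 24 and 30 are used below.

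**2. Does the plan expect change without FMT?** For gut function, yes. Inclusion requires intra-abdominal hypertension (IAH), and the Primary Endpoint section defines normal function as excluding it, so nobody is normal at entry. The plan assumes 50% recovered at one week in controls.

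As an illustration, take an exact before/after test (McNemar) on that course. All discordant pairs go one way, so k recoveries give P = 2 × 0.5^k. Five give 0.0625 and six give 0.031, so at least six are needed. With a 50% recovery rate, the probability of six or more is 0.997 at n = 24 and above 0.999 at n = 30. A before/after test would thus be significant almost surely in an arm that received no FMT. This is not a planned test of the primary endpoint; it only shows what such a test responds to.

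**3. The markers.** The documents give no mean change or SD for DAO, endotoxin, CRP or PCT. Let d be the change shared by both arms, in SDs of the within-patient change, with no FMT effect. The range of d is an assumption. The chance p that one arm's paired t test is significant comes from the noncentral t with n − 1 degrees of freedom and noncentrality d√n. The arms are independent, so the chance that FMT is significant and saline is not is p(1 − p).

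| d | n = 24: p | n = 24: p(1 − p) | n = 30: p | n = 30: p(1 − p) |
|---|---|---|---|---|
| 0 | 0.050 | 0.048 | 0.050 | 0.048 |
| 0.2 | 0.156 | 0.131 | 0.185 | 0.151 |
| 0.3 | 0.291 | 0.206 | 0.355 | 0.229 |
| 0.4 | 0.467 | 0.249 | 0.563 | 0.246 |
| 0.5 | 0.650 | 0.227 | 0.754 | 0.186 |
| 0.8 | 0.963 | 0.035 | 0.988 | 0.011 |

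The product p(1 − p) cannot exceed 0.25. It reaches that value when p = 0.5, which is at d of about 0.4 (0.37 at n = 30).

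**4. Between-arm tests under the same conditions.** In 40,000 simulated trials per setting (n = 24 and 30; d = 0, 0.3, 0.5 and 0.8; baseline to week-1 correlation assumed to be 0.5), three analyses were compared: the t test on week-1 values, the t test on change scores, and baseline-adjusted ANCOVA. Each rejected in 0.048 to 0.052 of trials. The shared change cancels between arms.

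**The case against.** The strongest reply is that the plan already contains the right tests. The same paragraph specifies valid between-arm comparisons and relative risks, and the trial is sized on a between-arm difference. A paired P value is a correct test of change over time and misleads only if someone reads it as a treatment effect. No sentence says that it will be read so. This stands. A reader might infer that the plan judges FMT by within-arm significance, or that the randomised comparison is missing for the markers; the documents support neither. What remains is that they do not exclude that use and apply one significance rule to both kinds of test.

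Three further limits also stand.

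- The plan does not say that the tests are run within each arm. That is the likeliest reading, but they could be run on pooled arms. A pooled before/after test is no more informative about FMT against saline.
- A reader might infer that patients enter at their worst and that every marker must then improve. Entry in gastrointestinal failure supports this for gut function only. Onset may be up to two weeks earlier, patients are not selected on any of the four markers, and the 50% control recovery concerns the primary endpoint.
- The FMT-only pattern is not common throughout the range. If both arms improve strongly, both tend to be significant, and the saline arm itself shows that the change is not specific to FMT. It is also tempting to multiply the risk over four markers as if they were independent. The plan groups DAO with endotoxin and CRP with PCT, so independence is doubtful and no such figure is relied on here.

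Finally, this might seem to be settled by adding a baseline-adjusted comparison. That would improve the between-arm analysis but leave the paired tests and their threshold in place.

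**Conclusion.** The point holds as a gap in the analysis rules. The plan sets paired tests, most plausibly before/after tests, at the same 0.05 as the between-arm tests and does not say which result supports a claim about FMT.

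Its size depends on an assumed shared change. Over 0.2 to 0.8 SD with no FMT effect, a single-arm result in the FMT group is significant in 16% to 96% of trials at 24 per arm and 19% to 99% at 30. The FMT-only pattern has a probability of at most about 25% per marker, highest at moderate change and 1% to 4% at 0.8 SD. These figures assume paired t tests, normally distributed changes and the same change in both arms.

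The consequence is confined to secondary and mechanistic endpoints. It would be wrong to infer that the primary result is compromised: that is a binary comparison between arms, which these tests do not touch. The sample size needs no change on this account. The correction is worth making because it limits what may be concluded on gut barrier, inflammation and microbiota.

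**What to change.** Amend the paired-test sentence in Statistical analysis to say two things.

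1. Within-arm changes in blood markers and microbiota are descriptive. They are reported as mean or median change with a 95% CI and are not judged against the 0.05 rule.
2. Any conclusion about FMT on these endpoints rests only on the comparison between arms. Preferably this compares week-1 values adjusted for baseline (ANCOVA, on a transformed or rank scale if skewed) and reports the between-arm difference with its 95% CI.

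Deleting the paired analyses is not necessary; stating their role is enough.

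The cost is a sentence or two of wording. No data and no power for FMT against saline are lost. The one real downside is that within-arm P values can no longer be cited as evidence. If analyses have already been run, the same rule can govern the report, identified there as a later clarification.
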